13 APPENDIX 5: CRITERIA BASED ON HY'S LAW

The following criteria for potential Hepatotoxicity are based on Hy's law. For criterion which requires multiple parameters to have a certain value (e.g., ALT>3x ULN and TBIL (total bilirubin)> 2xULN), all lab parameters values must be from samples with the same sample collection date.

ALT exceeds thresholds

- $\geq 3x$ ULN to $< 5x$ ULN
- $\geq 5x$ ULN to $< 8x$ ULN
- $\geq 8x$ ULN to $< 10x$ ULN
- $\geq 10x$ ULN

AST exceeds thresholds

- $\geq 3x$ ULN to $< 5x$ ULN
- $\geq 5x$ ULN to $< 8x$ ULN
- $\geq 8x$ ULN to $< 10x$ ULN
- $\geq 10x$ ULN

ALT or AST exceeds thresholds

- $\geq 3x$ ULN to $< 5x$ ULN
- $\geq 5x$ ULN to $< 8x$ ULN
- $\geq 8x$ ULN to $< 10x$ ULN
- $\geq 10x$ ULN

Other criteria

- Total Bilirubin (TBIL) $> 2x$ ULN
- ALP $> 1.5x$
- (ALT or AST $> 3x$ ULN) and (TBIL $> 2x$ ULN or INR > 1.5)*
- (ALT or AST $> 3x$ ULN) and TBIL $\geq 2x$ ULN and ALP $< 2x$ ULN*

*Criterion which requires multiple parameters to have a certain value (e.g., "and"), it is assumed that all lab parameter values are from the same sample.

QMD Ref: CCI	Governing QMD: CCI
Confidentiality Statement	
CCI	

80046695-study-11.01.01-20240109-sap_v3.0

Final Audit Report

2024-01-10

Created:	2024-01-09
By:	PPD
Status:	Signed
Transaction ID:	PPD

"80046695-study-11.01.01-20240109-sap_v3.0" History

-  Document created by PPD
2024-01-09 - 10:33:30 PM GMT
-  Document emailed to PPD) for signature
2024-01-09 - 10:34:24 PM GMT
-  Document emailed to PPD for signature
2024-01-09 - 10:34:25 PM GMT
-  Document emailed to PPD for signature
2024-01-09 - 10:34:25 PM GMT
-  PPD authenticated with Adobe Acrobat Sign.
2024-01-09 - 10:34:57 PM GMT
-  Document e-signed by PPD
Signing reason: I am the author of this document
Signature Date: 2024-01-09 - 10:34:58 PM GMT - Time Source: server
-  Email viewed by PPD
2024-01-09 - 10:50:46 PM GMT
-  PPD authenticated with Adobe Acrobat Sign.
Challenge: The user opened the agreement.
2024-01-09 - 10:51:02 PM GMT
-  PPD authenticated with Adobe Acrobat Sign.
2024-01-09 - 10:52:41 PM GMT
-  Document e-signed by PPD
Signing reason: I am the reviewer of this document
Signature Date: 2024-01-09 - 10:52:43 PM GMT - Time Source: server

 Email viewed by PPD

2024-01-10 - 2:16:46 PM GMT

 PPD authenticated with Adobe Acrobat Sign.

Challenge: The user completed the signing ceremony.

2024-01-10 - 2:17:35 PM GMT

 Document e-signed by PPD

Signing reason: I approve this document

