10. Hematology, serum chemistry, coagulation and urinalysis assessments will be performed locally according to the Schedule of Events throughout the study. Hematology assessments will include complete blood count (CBC) with 5-part differential, hemoglobin, and platelet count. Chemistry assessments will include the following: sodium, potassium, chloride, bicarbonate (or total carbon dioxide), blood urea nitrogen (BUN), creatinine, glucose, albumin, total protein, aspartate transaminase (AST/serum glutamic oxaloacetic transaminase [SGOT]), alanine transaminase (ALT/serum glutamic pyruvic transaminase [SGPT]), bilirubin (at least total and direct, or total and indirect), alkaline phosphatase, magnesium, phosphorous, calcium, creatine kinase (CK), amylase, and lipase. Coagulation studies include international normalized ratio (INR) and activated partial thromboplastin time (aPTT). If coagulation studies are within the normal range through C3D1 then they can be discontinued and obtained only as clinically indicated. Urinalysis (dipstick) will include pH, specific gravity, protein, ketone, glucose, urobilinogen, and occult blood.
11. Troponin T will be obtained at screening, C1D1, C2D1, and at the End-of-Treatment visits, only.

12. The pregnancy test will be performed locally and must be a beta-human chorionic gonadotropin ( $\beta$ -HCG) test, and either urine or serum can be used. Women who are not of childbearing potential (status post-hysterectomy, status post-bilateral oophorectomy, or post-menopausal [defined as amenorrhea for at least 12 months]) and men do not need to have the test performed. Women of childbearing potential at study start must also complete the pregnancy test once every 12 weeks thereafter (i.e., C4D1, C7D1, etc.) and at the End-of-Treatment visit. If required by local standard medical practice, more frequent pregnancy testing is allowed.
13. Echocardiogram or multiple gated acquisition (MUGA) scan will be performed at screening and once every 12 weeks after study start (i.e., C4D1, C7D1, etc.) and at the End-of-Treatment visit. Echocardiograms or MUGA scans will be performed locally in accordance with the institution's standard practice. The same modality should be used throughout the study.

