4.15.2 Laboratory Data

QMD Ref: CCI	Governing QMD: CCI
Confidentiality Statement	
CCI	

CCI		Sponsor: Theseus Pharmaceuticals, Inc.	
CCI		Protocol Number: THE630-21-101	
STATISTICAL ANALYSIS PLAN. PHASE 2-3-4			

Laboratory samples will be analyzed by local laboratories. For reporting purposes, lab parameters will be reported using SI units.

Each measurement (continuous data) will be classed as below, within, or above normal range, based on ranges supplied by the laboratory used. To identify laboratory values of potential clinical importance, National Cancer Institute Common Terminology Criteria for Adverse Events (CTCAE) will be used to assign grades for select laboratory parameters where applicable (See [Appendix 4](#)). A shift table representing two-way frequency tabulation for baseline and the worst post-baseline value according to the CTCAE grade, by cohort and overall, will be provided. For analysis purpose, patients with a lab parameter value that does not meet CTCAE criteria (e.g., value is within normal range) at baseline or any time post-baseline, will be assigned a Grade of 0 for said visit.

The incidence of patients meeting Hy’s law criteria will be summarized for any time, post-baseline (See [Appendix 5](#)).

A listing of any abnormal laboratory measurements recorded throughout the study will be presented.

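### SAP Appendix 5 ties both Hy's law composites to one collection date, so a patient whose ALT and AST are back to ≤3× ULN when bilirubin or INR crosses its cut-off is lost from the combined count

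*SAP*

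**What the plan says.** SAP Section 4.15.2 sets the reporting period: "The incidence of patients meeting Hy’s law criteria will be summarized for any time, post-baseline". The criteria are in SAP Appendix 5, which presents its whole list as criteria for potential hepatotoxicity. The list has two kinds of row.

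- **Single-parameter rows.** These are ALT tiers, AST tiers and ALT-or-AST tiers starting at 3× ULN, total bilirubin above 2× ULN, and an ALP row. None depends on the timing of another test. INR has no row of its own.
- **Two composites.** The first is ALT or AST above 3× ULN together with bilirubin above 2× ULN or INR above 1.5. The second is ALT or AST above 3× ULN, bilirubin at or above 2× ULN and ALP below 2× ULN. Both carry an asterisk.

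The opening text of the appendix says that for multi-parameter criteria "all lab parameters values must be from samples with the same sample collection date". The footnote to the asterisk is narrower: "it is assumed that all lab parameter values are from the same sample".

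The results go to Table 14.3.4.5 (counts) and Listing 14.3.4.6 (patients). The SAP does not say which Appendix 5 rows place a patient in that listing.

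On INR, footnote 10 to the protocol's Schedule of Events says: "If coagulation studies are within the normal range through C3D1 then they can be discontinued and obtained only as clinically indicated".

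**The concern.** A Hy's law composite exists to join a transaminase rise to a loss of liver function in the same patient. If bilirubin or INR crosses its cut-off only after ALT and AST have returned to 3× ULN or below, the two events fall on different dates and the composite is not met. Section 4.15.2 asks whether a patient met the criteria at any time after baseline, but for the composites this reduces to meeting every part on a single date.

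The study is first-in-human, safety is the primary Phase 1 endpoint, and 32 patients were enrolled (SAP Section 1). The composites are the only planned rows that join the parameters, so a zero there would be read as no such case. The two wordings of the timing rule also leave the programmer to choose. Protocol Table 8 places INR under coagulation and ALT under chemistry, so a literal same-sample rule could leave the INR limb impossible to satisfy.

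**Working it through.** The plan states no figure for this point, so there is none to reproduce. The check has three parts.

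**1. The rows applied to three hypothetical patients.** The visit days are the protocol's laboratory days (Sections 6.3.1 to 6.3.9): Days 1, 8, 15, 29 and 57. The laboratory values are assumed. AST is taken as ≤3× ULN throughout and ALP as below 2× ULN.

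| Patient | ALT peak | Visit with bilirubin >2× ULN | Same-date composites | Separate rows met |
|---|---|---|---|---|
| A | 9× on Day 15 | Day 29: ALT 4.5×, bilirubin 2.6× | both met | ALT ≥8 to <10×; bilirubin >2× |
| B | 9× on Day 15 | Day 29: ALT 2.4×, bilirubin 2.6× | neither met | the same two |
| C | 9× on Day 29 | Day 57: ALT 2.1×, bilirubin 2.4× | neither met | the same two |

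Patient A shows that a falling ALT is not enough for a miss. The miss needs ALT and AST both ≤3× ULN on every date that bilirubin or INR is above its cut-off. If bilirubin may follow ALT >3× ULN within a window, B needs 29 − 15 = 14 days and C needs 57 − 29 = 28 days. B is missed with 7 days and found with 14, 28 or 30. C is missed with 7 or 14 and found with 28 or 30.

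**2. How often a window would help.** Everything here except the visit days is assumed: an ALT peak of 5-15× ULN and a bilirubin peak of 2.5-5× ULN; a linear rise over 5 days, then exponential decay; a bilirubin half-life of 7 days; no unscheduled tests. The table gives the share of simulated cases found when ALT peaks are uniform over Days 6-112.

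| Bilirubin lag | ALT half-life | Same date | 0 to +30 days | Gain (points) |
|---|---|---|---|---|
| 7 d | 3 d | 7% | 13% | 6 |
| 7 d | 7 d | 33% | 35% | 2 |
| 14 d | 3 d | 0% | 9% | 9 |
| 14 d | 7 d | 10% | 17% | 7 |

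For ALT peaks confined to Days 6-28 the gain is about 9 to 42 points. With 28-day sampling alone the two rules find about the same few cases. Continuous weekly sampling would give much larger contrasts (0% against about 95% at worst), but that is not this protocol's schedule. The percentages shift by several points with the resting level assumed before and after the rise, so only their order of size should be used.

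**3. What one missed case does to the table.** With n = 32 and exact (Clopper-Pearson) limits, one case is 1/32 = 3.1% (95% CI 0.1 to 16.2). If it is missed, the row reads 0/32 = 0%, with upper limit 1 − 0.025^(1/32) = 10.9%.

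**The case against.** The strongest reply is that nothing disappears. A reader might infer that a patient like B or C is counted as having no potential hepatotoxicity. Appendix 5 does not support that, because the single-parameter rows belong to the same list and both patients count in an ALT tier and in the bilirubin row.

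Nor are Table 14.3.4.5 and Listing 14.3.4.6 the only liver displays. Table 14.3.4.3 gives chemistry grade shifts, Table 14.3.4.4 gives coagulation shifts including INR, Listing 14.3.4.1 gives abnormal values, and the adverse event tables stand beside them. With a normal baseline, ALT of 9× ULN is Grade 3 in SAP Appendix 4.

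A reader might also infer that such a patient is kept out of Listing 14.3.4.6. The SAP does not say so. The listing's title uses the term that Appendix 5 applies to every row, so entry is possible.

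On INR, testing after C3D1 may stop only if results were normal, and it continues when clinically indicated. Bilirubin alone also satisfies the first composite. Finally, neither the lag between the two rises nor a 30-day window has a source in these documents.

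All of this stands, and it limits the harm. It does not restore the link: none of these displays joins the two rises, and with most other listings dropped in SAP version 3.0 a reader would have to rebuild the sequence by hand from the abnormal-value listing. A patient whose only later signal is INR has no separate row in the Appendix 5 list for it.

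**Conclusion.** The concern holds in a limited form. The composites miss a sequential rise when ALT and AST are both ≤3× ULN on every date that bilirubin or INR is above its cut-off. What is lost is the link between the rises, not the values. The gain from a window is about 2 to 9 percentage points for ALT peaks over Days 6-112 and about 9 to 42 points for peaks in Days 6-28, where visits are closest together. Those figures rest on assumed curves, lags and half-lives and on scheduled visits only; tests repeated after a rise would change them. How many of the 32 patients are affected, if any, cannot be known from the documents. This is a cheap improvement to a safety table. It does not show that the plan hides liver injury.

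**What to change.** In SAP Appendix 5:

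1. Keep both same-date composite rows.
2. Add a windowed row for each, with its own bilirubin cut-off unchanged. The bilirubin rise (or INR above 1.5, for the first composite) must fall on the same day as, or within a stated number of days after, any post-baseline ALT or AST above 3× ULN. Thirty days is an example and an assumption. It spans the nominal 28-day visit spacing, but with the ±7-day visit window from Cycle 3 two consecutive visits can be 28 + 7 + 7 = 42 days apart, so the chosen length should be justified.
3. For the windowed ALP-qualified row, use ALP on the date of the most recent qualifying ALT or AST value on or before the bilirubin date.
4. Reconcile the same-date wording with the same-sample footnote.
5. State that a patient meeting either the same-date or the windowed composite enters Listing 14.3.4.6.

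This changes reporting only. It needs a few lines of code and a short SAP edit, and it may bring a few extra patients to review. It adds no INR data where INR was not drawn.
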